6.4 EOT Visit

This visit should occur 30 days (+/- 3 days) after brigatinib treatment stops for whatever reason (adverse event, progression, or at discretion of the investigator). Patients who have an ongoing grade 4 AE or SAE at the time of discontinuation from treatment will be contacted every 2 weeks until the event is resolved, determined to be irreversible by the investigator, or until the patient begins an alternate form of treatment.

NOTE: The first EOT follow up visit is to be performed 30 days (+/- 3 days) after the date a participant receives the last dose of study drug. The date of the EOT visit will not match the date the last dose of study drug was administered and should be entered accordingly on the eCRF/EDC system.

Clinical evaluation: focused medical history on symptoms/adverse events, comprehensive physical examination (to include weight), vital signs, ECOG performance status.

Laboratory studies:

- **Hematology**: CBC with differential
- Serum Chemistries: blood urea nitrogen (BUN), creatinine, bilirubin, ALT (SGPT), AST (SGOT), alkaline phosphatase, amylase, creatinine phosphokinase (CPK)

AE: Adverse events will be assessed according to the NCI CTCAE v. 4.0. All SAEs (see section 7.0) ongoing 30 days or more after last dose of study drug is administered should be followed at least every 4 weeks until they resolve to baseline (or CTCAE grade ≤ 1), stabilize, or are considered to be chronic/irreversible regardless of causality. See also section 7 for documentation of AEs/SARs, when applicable, for patients remaining in the study after transition from cohort A or B to cohort C.

Concomitant medications: Review for any changes since previous visit.

Tissue acquisition: At time of progression on study therapy, biopsy will be repeated in patients who consent to this optional biopsy; see section 6.6 and laboratory manual for additional details.

Blood sample: A blood sample for ctDNA will be requested at time of progression on current therapy. Time of progression for cohort C means patient's further progression (as indicated by CT scan) from their entry into cohort C); see section 6.6 and the laboratory study for additional details.

Cohort C: For patients enrolling in cohort C from cohorts A or B end of treatment is not required; however:

- The EOT section of the eCRF form must still be completed;
- To avoid repeating assessments, EOT (cohort A or B) and screening (cohort C) assessments (including CT scans, brain MRIs, etc.), reasonable efforts should be taken to perform these assessments as standard of care at EOT to be used for cohort C screening assessments;
- Data relevant to each cohort's participation in the study will be independent according to their cohort assignment and recorded on each applicable eCRF for (i.e., EOT for cohort A or B, screening for cohort C).
- In the event of active AE's which continue past the subjects transition to cohort C, and continuing past the transition date, they are to be recorded under the new Subject number within the Medical History Log, to be updated upon change in AE. severity or status.

6.5 **Post-Treatment/Follow-up Assessments**

Long-term follow up will occur every 3 months from the last administration of protocol-directed therapy for up to 2 years or until death, whichever occurs first. Subsequent therapy and survival status will be documented.

Each cohort A, cohort B and cohort C participant's follow-up data will be captured from their time of enrollment in the cohort (for up to 2 years, or until death, whichever occurs first).

NOTE:

- The first post-treatment follow-up is to be performed 30 days (+/- 3 days) after the date a participant receives the last dose of study drug.
- The date of the EOT visit will not match the date the last dose of study drug was administered and should be entered accordingly on the eCRF/EDC system.
- Follow-up may occur via review of medical records, and on-site visits are not required. To maintain the every 3 month follow-up schedule, these methods should be used for long-term follow up of cohort A or B participants, when their participation and treatment in the study continues as a cohort C participant.

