1.0 BACKGROUND AND RATIONALE

1.1 Study Synopsis

This multicenter phase II trial will evaluate brigatinib (AP261136) in patients with advanced non-small cell lung cancer (NSCLC) harboring an anaplastic lymphoma kinase (ALK) rearrangement, previously treated with a next generation ALK inhibitor such as ceritinib or alectinib.(Shaw et al. 2014; Soria et al. 2017; Peters et al. 2017; Hida et al. 2017) Ceritinib and alectinib are referred to as 'next generation," and are approved by the Food and Drug Administration (FDA) for patients with a confirmed ALK rearrangement (referred to as ALK+) who have progressed on or are intolerant of crizotinib, and alectinib and ceritinib is approved for treatment naïve patients. Alectinib, ceritinib, and crizotinib currently are recommended by the National Comprehensive Cancer Network (NCCN) as first-line therapy with category 1 recommendations; alectinib is the preferred therapy.() In addition, multiple other next generation inhibitors are in development. Brigatinib has also demonstrated significant activity in patients who have progressed on crizotinib, with responses reported for both intracranial and extracranial disease.(Kim et al. 2017) The activity of brigatinib in patients who have disease progression after ceritinib or alectinib has not been prospectively investigated. Brigatinib was compared to crizotinib in phase 3 trial of treatment naïve patients, and was found a statistically significant improvement in progression-free survival.

There is increasing concern that patients who have been exposed to multiple therapies may have multiple mechanisms of resistance, including ALK dependent and ALK independent mechanisms of resistance. Therefore, patients will be divided into cohorts (A) patients who have progressed on multiple lines (>1) of ALK directed therapy, including at least one licensed or experimental next generation therapy (B) patients who have progressed on only alectinib.⁸ In an exploratory cohort (C) patients who tolerate but progress on 180mg brigatinib (as a part of the trial or as part of routine clinical care) will be treated with 240 mg brigatinib daily to determine if intra-patient dose escalation is safe and tolerable and is associated with greater activity at the higher doses.

Rationale for post alectinib cohort

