3.2 Inclusion criteria for cohort assignment

- **3.2.1** Cohort A: Progressive disease on any next generation ALK inhibitor except first line alectinib alone (eligible for study but assigned to cohort B) or brigatinib (any line). Patients who received previous therapy with lorlatinib will be assigned to cohort A.
- **3.2.2** Cohort B: Progressive disease on first-line therapy with alectinib, and no other ALK inhibitors
- **3.2.3** Cohort C: Previous treatment brigatinib at 180 mg daily for \geq 4 weeks without > grade 2 drug-related toxicities and with radiographic evidence of

progressive disease and no intervening systemic therapies such as chemotherapy, immunotherapy or another ALK inhibitor (radiation therapy allowed as intervening therapy).

3.2.4 Patients who are treated on cohorts A and B will be allowed to enroll in cohort C if they meet the inclusion and exclusion criteria. Patients are required to undergo a biopsy before enrollment in cohort C. Patients who change cohorts from A or B to cohort C should not have EOT assessments completed and do not discontinue brigatinib, and should complete a new registration form and will be given a new subject number

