7.3 Documentation of non-serious AEs or SARs

For non-serious AEs or SARs, documentation must begin from day 1 of study treatment and continue through the 30-day follow-up period after treatment is discontinued.

Collected information should be recorded in the Case Report Forms (CRF) for that patient. Please include a description of the event, its severity or adverse event grade, onset and resolved dates (if applicable), and the relationship to the study drug. Documentation should occur at least monthly.

For patients with two Subject Identification Numbers (SI#), resulting as participants in Cohort A or Cohort B, and then Cohort C (upon disease progression), each AE should be recorded as applicable to their cohort participation including the following:

- An original AE under their SI#1 should be completed (followed and recorded to resolution) under that cohort.
- AEs for Cohort C should be applicable to their participation under Cohort C:
 - a. AEs from SI#1 should be recorded once resolved under SI# 1.
 - b. AE history from the patient's SI#1 to be included as medical history for the patient under their SI# 2.
 - c. Original AEs under SI#1 that increase in severity to be recorded as a new AE under the patient's SI#2 (as cohort C).

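### For patients moving from cohort A/B to C, sections 6.4 and 7.3(c) record a worsening adverse event differently, so worsening at 240 mg can be missed in the cohort C AE data

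*Combined protocol and SAP*

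**What the plan says.** Section 3.2.4 lets cohort A and B patients enter cohort C. They receive a new subject number, "should not have EOT assessments completed and do not discontinue brigatinib". Section 7.3 calls the A/B number SI#1 and the cohort C number SI#2.

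For an AE that continues past the move, the Cohort C bullets of section 6.4 say it is to be "recorded under the new Subject number within the Medical History Log, to be updated upon change in AE. severity or status". The AE paragraph of the same section adds "See also section 7 for documentation of AEs/SARs, when applicable, for patients remaining in the study after transition" from A or B to C.

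Section 7.3 has its own list for these patients. Its first bullet reads "An original AE under their SI#1 should be completed (followed and recorded to resolution) under that cohort". Item (b) carries the AE history into the SI#2 medical history. Item (c) reads "Original AEs under SI#1 that increase in severity to be recorded as a new AE" under SI#2. AE collection must "continue through the 30-day follow-up period after treatment is discontinued".

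Section 8.3 names AE evaluation by CTCAE as a secondary endpoint, analyses each cohort on its own and provides general frequency tables. Its one sentence with AE descriptors (type, grade, attribution) has the association of survival with baseline covariates as its subject, which those descriptors cannot describe.

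**The concern.** Cohort C exists "to determine if intra-patient dose escalation is safe and tolerable" (section 1.1), and objective 2.2.1 asks for treatment-related AEs to be characterised at different doses. Entry to C requires at least four weeks at 180 mg "without > grade 2 drug-related toxicities" (section 3.2.3). A related AE carried into C is therefore normally grade 1 or 2, and if it later reaches grade 3 it will normally have done so at 240 mg. Among movers, this is one of the main ways in which toxicity of the higher dose would show.

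That same event, a rise in severity of a carried-over AE, is a medical-history update under 6.4 and a new AE under 7.3(c). A medical-history entry does not normally feed an AE table. A site that works from 6.4 would drop the worsening from the AE data of the cohort set up to detect it, while following a stated instruction.

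**Working it through.** **1. The instructions side by side.** Take a related AE that is grade 2 at the move and becomes grade 3 at 240 mg.

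| What the site does | SI#1 record (A/B) | SI#2 medical history | SI#2 AE record | Effect on grade ≥3 tables |
|---|---|---|---|---|
| 6.4 only; SI#1 grade left as it was | grade 2 | updated to 3 | none | missing from C |
| 6.4 only; SI#1 followed to resolution and regraded | grade 3 | updated to 3 | none | missing from C, counted in A/B |
| 7.3 including (c); SI#1 regraded | grade 3 | grade 2 | new AE, grade 3 | counted in C and again in A/B |
| 7.3 including (c); SI#1 grade left as it was | grade 2 | grade 2 | new AE, grade 3 | correct |

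Only the last row is right. Section 7.3(c) leads part of the way there, but no text fixes the SI#1 grade at the first 240 mg dose. The 30-day collection limit does not do so either: it runs from discontinuation, and movers do not discontinue. The errors lean one way, because events are lost from C or higher grades are added to A/B.

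**2. Size per patient.** The plan gives no figure for AE rates, for the number of movers or for AEs that span a move, so there is none to reproduce. Cohort sizes come from section 8.2: 20 at stage 1 and 40 in full. For k misfiled patients in a cohort of n, the shift in an AE row is 100 × k/n points.

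- n = 40: 100 × 1/40 = 2.5 points per patient.
- n = 20 (cohort stopped after stage 1): 100 × 1/20 = 5.0 points per patient.

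**3. Scale.** Section 1.1 lists grade 3 or 4 events in 15 phase 1/2 patients on 240 mg daily, 300 mg daily or 120 mg twice daily. Most rows are 7% or 13%. In a cohort of 40 these are 0.07 × 40 = 2.8 and 0.13 × 40 = 5.2 patients. One misfiled patient is then 1/2.8 = 36% or 1/5.2 = 19% of such a row.

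**4. Illustration, assuming 1 to 3 misfiled patients** (exact Clopper-Pearson 95% intervals):

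| True row | Loses 1 | Loses 2 | Loses 3 |
|---|---|---|---|
| 5/40 = 12.5% (4.2 to 26.8) | 10.0% (2.8 to 23.7) | 7.5% (1.6 to 20.4) | 5.0% (0.6 to 16.9) |
| 3/40 = 7.5% (1.6 to 20.4) | 5.0% (0.6 to 16.9) | 2.5% (0.1 to 13.2) | 0% (0 to 8.8) |

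Each reduced rate lies inside the interval around the true row, except 0% for the 3/40 row, which falls below its lower limit of 1.6%.

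**The case against.** The strongest reply is that section 7.3 is one sequence: complete the AE under SI#1, copy it as history under SI#2, and open a new SI#2 AE if it worsens. The 6.4 log entry is then the copying step, and updating a log does not forbid a new AE. Section 6.4 also sends the reader to section 7 for exactly these patients, and both sections say that data belong to the cohort in which they arise. Much of this stands. A reader might infer that the protocol names three rival destinations for one event. It does not, because the steps in 7.3 are cumulative. The direct clash is one clause of 6.4 against 7.3(c). That clash remains: 6.4 gives a complete instruction for a change in severity, does not mention a new AE, and refers to section 7 only when applicable.

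A reader might also infer that a planned comparison of 240 mg with 180 mg is biased. The documents plan none: 2.2.1 asks for characterisation, and 8.3 keeps the cohorts apart. What is affected is the descriptive AE summary of each cohort.

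Other records would limit the harm. Under section 4.5 a related grade 3 event in C brings a hold, and discontinuation if it lasts seven days or more or a second one occurs. Reasons for discontinuation go on the eCRF (4.12), and serious events have their own 24-hour route (7.4.2). These leave traces of the worst events, but they do not put a non-serious worsening into the AE table, and 7.4 has no rule for movers.

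Finally, the faulty sentence in 8.3 does not cause the recording conflict. Correcting it would not tell a site which form to use. It is a separate drafting error whose intent is fairly clear.

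**Conclusion.** The inconsistency is real and narrow. Followed as written, 6.4 leaves worsening at 240 mg out of the cohort C AE data, and the open-ended SI#1 record allows the higher grade to be counted under A/B. The effect is 2.5 points per affected patient in a cohort of 40, or 5.0 in a cohort of 20.

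The total cannot be stated, because the documents give neither the number of movers nor the number of AEs that span a move; the range of 1 to 3 patients is an assumption. Patients who enter C from routine care are unaffected, as are movers with no active AE. Shifts of this size are mostly within sampling error for one cohort. The case for acting is that the error runs in one direction, falls on the cohort meant to test tolerability, and is easily avoided. ORR and the Simon decision rule do not depend on it. This should be corrected, but nothing in the design turns on it.

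**What to change.** - **Section 6.4:** replace the clause on updating the log with: *any increase in severity on or after the first 240 mg dose is recorded as a new AE under SI#2 per 7.3(c)*.
- **Section 7.3:** add: *the SI#1 record keeps the worst grade reached before the first 240 mg dose; the resolution date may be added later*.
- **Patients already moved:** raise one data query. Look for severity updates in the SI#2 Medical History Log and enter them as AEs, and check SI#1 records for grades dated after the first 240 mg dose.
- **Section 8.3 (separate correction):** replace the misattached sentence with: *AEs with onset or worsening in a cohort will be summarized for that cohort by type, worst grade and attribution*.

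The cost is wording in three sections, a CRF completion note and one query. No visits or tests are added. The drawback is that worsening soon after the move is charged to 240 mg even if it would have happened anyway. For movers, grading under A/B also stops at the first 240 mg dose, so they have no 30-day post-treatment period in A/B.

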6.6 Correlative Studies Procedures

6.6.1 Tumor Biopsies

Tumor biopsy (core biopsy) after progression on previous ALK inhibitor and within 60 days prior to D1 of study treatment is mandatory i.e., if tissue available from pre-study biopsy, this tissue will be accessed for correlative studies, otherwise, patients must consent to tumor biopsy to meet eligibility criteria. All subjects must consent to provide tumor blocks or slides. If archival tissue is not available and biopsies to obtain fresh tumor tissue cannot be performed with minimal risk to the subject, subjects may be permitted to enroll on the study with prior approval of the Study PI. Patients who undergo biopsies and subsequently found to have insufficient will be permitted to enroll on the study with prior approval of the study PI. Patients who have standard of care next-generation sequencing performed are able to enroll on the study, but must have sufficient tumor tissue to participate in the study (i.e. next generation sequencing cannot be substituted for providing tumor sample).

Core biopsies may be performed by clinical personnel trained in this procedure for standard of care collections. The number of passes made through the tumor per biopsy will be determined by the treating physician and the physician performing the biopsy procedure with primary consideration being safety. The tissue collected will be divided into aliquots (depending on size of collection, up to 4 aliquots per collection) to enable enough tissue for planned correlative studies. Additional details regarding processing, storing and handling tissue will be provided in a separate laboratory manual.

Biological samples collected for the study will be shipped to and stored in the research laboratories at the University of Colorado until the completion of the study. With patient consent, any remaining tumor tissue after protocol specific studies are complete will be stored for future research concerning lung cancer.

6.6.2 Blood Sample for ctDNA

Blood samples from enrolled patients will be evaluated via next generation sequencing for circulating tumor DNA (no germline studies will be performed). If possible, blood sample at progression should be performed while patient is still taking brigatinib; if drug is discontinued, the blood sample should be performed within 2 days of discontinuation.

6.6.3 Risks of Correlative Study Procedures-Biopsy

Liver (core needle biopsy):

Likely: local discomfort and minor bleeding

Less likely: moderate or major bleeding, need for blood transfusion, hospitalization due to bleeding or other complications, infection, bowel perforation or damage to adjacent organs

Lung (core needle biopsy in all patients):

Likely: local discomfort and minor bleeding

Less likely: pneumothorax, hemothorax, intraparenchymal hemorrhage, hemoptysis, bronchopleural fistula, air embolism, and vascular injury

In order to minimize the risk of a biopsy, only qualified personnel will perform these procedures. Prior to the procedure, the physician performing the procedure will discuss the risks with each study participant, answer any questions, and obtain separate procedure consent. For biopsies of lesions that are not superficial and clearly palpable, imaging studies such as CT scan will be used to guide the biopsy in order to minimize the risk of damage to adjacent structures. After liver biopsies, patients will be observed for approximately 4 hours (range 4-6 hours) after the procedure, or per institutional standard guidelines. Less than the goal quantity of tissue is acceptable for each type of biopsy, and will be left to the clinical judgment of the physician performing the procedure.

6.6.4 Risks of Correlative Study Procedures-Anesthesia

Local Anesthesia

All biopsy procedures require local anesthesia using lidocaine, xylocaine, or related compounds. There is a small risk of an allergic reaction associated with these drugs. In order to minimize the risk of local anesthesia, only qualified personnel will perform the biopsy procedure. Patients will be queried if they have had previous allergic reactions to local anesthetics.

Intravenous Conscious Sedation

Certain biopsy procedures may require IVCS. IVCS is a minimally depressed level of consciousness that retains the patient's ability to maintain a patent airway independently and continuously and respond appropriately to physical stimulation and verbal commands. The medications used to induce conscious sedation include the benzodiazepine midazolam and the opioid agonist fentanyl, as per standard of care. IVCS is performed once over a 30-60 minute period, and may require administration of multiple doses of each agent over this time-frame.

Rarely, IVCS will last longer than 60 minutes.

Midazolam:

See http://www.drugs.com/pro/midazolam-injection.html for complete prescribing information on midazolam, including complete information on risks associated with its use.

The risks of midazolam include respiratory depression and respiratory arrest, especially when used for sedation in non-critical settings. Respiratory arrest could require intubation. In very rare cases, when this was not recognized promptly and treated effectively, death or hypoxic encephalopathy has resulted. Other serious cardiorespiratory adverse events have occurred after administration of midazolam, including airway obstruction, oxygen desaturation, apnea, and cardiac arrest, rarely resulting in death or permanent neurologic injury. There have also been rare reports of hypotensive episodes requiring treatment, particularly in patients with hemodynamic instability. Agitation, involuntary movements, hyperactivity and combativeness have been reported in adults patients treated with midazolam.

Concomitant use of midazolam with other respiratory depressants like fentanyl may increase the risk of hypoventilation, airway obstruction, desaturation or apnea, and may contribute to profound and/or prolonged drug effect. Prolonged sedation may also be seen midazolam is administered concomitantly with drugs known to inhibit the P450 3A4 enzyme system such as cimetidine, erythromycin, diltiazem, verapamil, ketoconazole and itraconazole.

Adverse effects reported after intravenous administration of a single dose when used as a sedative include the following (percentage is percentage of adult patients with adverse events): hiccoughs (3.9%), nausea (2.8%), vomiting (2.6%), coughing (1.3%), "oversedation" (1.6%), headache (1.5%), and drowsiness (1.2%). In addition, the following local effects at the site of the injection have been reported: tenderness (5.6%), pain during injection (5.0%), redness (2.6%), induration (1.7%), and phlebitis (0.4%).

Additional rare (<1.0%) adverse events occurring when midazolam is used as a sedative include:

- Respiratory (laryngospasm, bronchospasm, dyspnea, hyperventilation, wheezing, shallow respirations, airway obstruction, tachypnea);
- Cardiovascular (bigeminy, premature ventricular contractions, vasovagal episode, bradycardia, tachycardia, nodal rhythm);
- Gastrointestinal (acid taste, excessive salivation, retching);
- CNS/Neuromuscular (retrograde amnesia, euphoria, hallucination, confusion, argumentativeness, nervousness, anxiety, grogginess, restlessness, emergence delirium or agitation, prolonged emergence from anesthesia, dreaming during emergence, sleep disturbance, insomnia, nightmares, athetoid movements, seizure-like activity, ataxia, dizziness, dysphoria, slurred speech, dysphonia, paresthesia);
- Special Senses (blurred vision, diplopia, nystagmus, pinpoint pupils, cyclic movements of eyelids, visual disturbance, difficulty focusing eyes, ears blocked, loss of balance, light-headedness);
- Integumentary (hive-like elevation at injection site, swelling or feeling of burning, warmth or coldness at injection site);
- Hypersensitivity (allergic reactions including anaphylactoid reactions, hives, rash, pruritus);
- Miscellaneous (yawning, lethargy, chills, weakness, toothache, faint feeling, hematoma).

Fentanyl

See http://www.drugs.com/pro/fentanyl-injection.html for complete prescribing information on fentanyl (Duragesic®), including complete information on risks associated with its use.

Fentanyl may cause muscle rigidity, particularly involving the muscles of respiration. Skeletal muscle movements in the extremities, neck and external eye have also been reported with fentanyl; rarely, these have been strong enough to pose patient management problems. Fentanyl may also produce euphoria, miosis, bradycardia and bronchoconstriction, as seen with other narcotic analgesics. The most common serious adverse reactions reported with fentanyl include respiratory depression, apnea, rigidity, and bradycardia. If these remain untreated, respiratory arrest, circulatory depression or cardiac arrest could occur. Other adverse reactions that have been reported are hypertension, hypotension, dizziness, blurred vision, nausea, emesis, laryngospasm and diaphoresis.

The risks of IVCS also include inhibition of the gag reflex and concomitant risk of aspiration and allergic reactions to the sedative or analgesic medications. The chances of serious risks from IVCS are small but real; for example, in a prospective study of 14,149 patients undergoing IVCS during upper gastrointestinal endoscopies, the rate of immediate cardiopulmonary events was 2 in 1000. The 30-day mortality was 1 per 2,000 cases. In this study, there was a strong association between lack of monitoring and use of high-dose benzodiazepines with adverse outcomes. There was also an association between the use of local anesthetic sprays to the oropharynx and the development of

pneumonia (Waring JP, B.T., Hirota WK, et al Gastrointestinal Endoscopy).

In order to minimize the risk of IVCS, only qualified personnel (M.D. and R.N) will be responsible for conscious sedation. A minimum of two individuals will be involved in the care of patients undergoing conscious sedation-the physician performing the biopsy procedure, and the individual (R.N.) who monitors the patients and his/her response to both the sedation and the procedure, and who is capable of assisting with any supportive or resuscitative measures. The room where the procedure utilizing IVCS takes place in the interventional radiology suite will have adequate equipment to provide supplemental oxygen, monitor vital signs, and maintain an airway should this be necessary. An emergency cart will also be immediately accessible to the room where the procedure is to take place, and emergency support services will be available on page. Patients will be screened and evaluated for their fitness to undergo conscious sedation by a trained physician. Patients with active cardiac disease are excluded from this study. No local anesthetic spray to the oropharynx will be necessary, given that endoscopy is not a planned procedure. Following the procedure, patients will be observed closely in the recovery room according to standard institutional guidelines.

6.6.5 Risks of Correlative Study Procedures-Blood Draws and IV Insertion Risks of Blood Draws and I.V. Insertion

Blood draws may be associated with slight discomfort from the needle-stick, localized erythema, bleeding/bruising, or soreness around the area where the needle is inserted. Insertion of an intravenous catheter (I.V.) has similar risks, in addition to a small risk of infection at the site where the needle is inserted.

In order to minimize the risk of blood draws and I.V. insertion, only trained personnel will perform these procedures, according to standard institutional guidelines.

